7.1.1. Selection of Concentrations in the Study

In this clinical study, four dose levels of DE-122 (0.5 mg, 1.0 mg, 2.0 mg or 4.0 mg) are being tested in subjects with refractory exudative AMD. Systemic exposure of DE-122 in this study given by a single IVT injection at dose levels up to 4.0 mg/eye is anticipated to be significantly lower than the systemic exposure in over 300 cancer subjects (most of whom received 10 mg/kg of TRC105 by weekly intravenous infusion). Therefore, no concerns regarding systemic toxicity are anticipated in this study.

In pre-clinical studies, the highest tested DE-122 IVT dose of 5 mg/monkey eye would correlate to 10 mg/eye in human eyes due to the difference in volume, hence the difference in vitreous volume between human and monkey (2:1 ratio) conveys a margin of safety.

The starting IVT dose of 0.5 mg utilized in this clinical study is only 1/10 (10%) of the 5 mg dose determined as safe in the single dose toxicity study in cynomolgus monkeys by IVT injection (and 1/20, or 5%, of the safe 5 mg dose taking into account differences in monkey and human vitreous volumes). The highest 4.0 mg dose tested in this clinical study is only 80% of the safe dose in monkeys (and 40% of that dose with differences in vitreous volume considered).

In the mouse model of laser-induced CNV efficacy study, animals were given an IVT injection of DE-122 at 0.5, 1.5 and 5.0 µg/eye. DE-122 inhibited CNV in a dose-dependent manner. The lowest effective dose was 0.5 µg/eye. Considering the vitreous volume difference between human and mouse (~1000:1 ratio), 0.5 mg/eye is considered a logical starting dose level for this initial clinical study. In addition, the 0.5 mg DE-122 IVT dose is 10 times lower than the tolerated dose of 5.0 mg/eye utilized in the single dose toxicity study in cynomolgus monkeys, aside from the margin of safety conferred by the difference in vitreous volume between monkey and human eyes described above.

7.2. Number of Subjects

Approximately 12 subjects (2 or 3 subjects in Cohort 1, 3 subjects each in Cohorts 2, 3 and 4) with refractory exudative age related macular degeneration will be enrolled at 5 sites. The final number of subjects enrolled may be adjusted based on the presence of dose limiting toxicities.

7.3. Treatment Assignment

Four dose levels of DE-122 will be administered by a single IVT injection in the study eye as noted in [Table 3](#).

Table 3: Dose Groups and Associated DE-122 Concentration

Dose Group	DE-122 Concentration
Cohort 1: 0.5mg	20 microliters of 25 mg/mL DE-122
Cohort 2: 1.0mg	40 microliters of 25 mg/mL DE-122
Cohort 3: 2.0mg	20 microliters of 100 mg/mL DE-122
Cohort 4: 4.0mg	40 microliters of 100 mg/mL DE-122

7.4. Dose Adjustment Criteria

The Safety Review Team will review safety parameters after the first subject in a given cohort has completed Visit 3 (Day 8±1). The remaining subjects in the cohort will receive the same dose if neither the safety criteria for adjusting or stopping doses ([Section 7.4.1](#)) nor the criteria for study termination ([Section 7.5](#)) preclude their treatment.

When the first 2 or 3 subjects in Cohort 1 and 3 subjects in other Cohorts have completed Visit 5 (Day 30±2), the Safety Review Team will again evaluate the safety parameters. If the safety criteria for adjusting or stopping doses and the criteria for study termination are not met, the first subject in the next cohort will receive the next higher DE-122 dose level.

The same safety evaluations will be performed for each cohort.

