7. INVESTIGATIONAL PLAN

7.1. Overall Study Design and Plan

This is an open-label, dose-escalating, sequential-cohort study assessing the safety, tolerability, immunogenicity, and bioactivity of a single IVT injection of 0.5 mg, 1.0 mg, 2.0 mg and 4.0 mg DE-122 injection administered in a total of approximately 12 subjects with refractory exudative AMD.

Approximately 12 subjects in four cohorts (2 or 3 subjects in Cohort 1, 3 subjects each in Cohorts 2, 3 and 4) will receive a single IVT injection of DE-122 in the study eye. Decisions regarding dose escalation will be based on the recommendations of the Safety Review Team consisting of an external Retina Specialist, the Medical Monitor, and the Drug Safety Physician. Dose-Limiting Toxicity response observed in any cohort will result in termination of the dose escalation.

The study is designed to include up to a 7-day screening phase and 90-day treatment/follow-up phase for each subject.

The first eligible subject in Cohort 1 will receive a single intravitreal injection of 0.5 mg DE-122 in the study eye and will be evaluated through Visit 3 (Day 8±1). The Safety Review Team will review the safety parameters and determine if the safety and tolerability are acceptable.

If acceptable, up to two additional eligible subjects in Cohort 1 will each receive a single intravitreal injection of 0.5 mg DE-122 in the study eye before starting Cohort 2. After the first 2 or 3 subjects in Cohort 1 have completed Visit 5 (Day 30±2), the Safety Review Team will review the safety parameters of the first 2 subjects in Cohort 1 and determine if the next dose (1.0 mg) will be administered to Cohort 2.

The same enrollment procedures will be followed for Cohort 2 (1.0 mg of DE-122), Cohort 3 (2.0 mg of DE-122) and Cohort 4 (4.0 mg of DE-122), however 3 subjects must be enrolled in these cohorts.

Rescue therapy with anti-VEGF medication may be allowed at Visit 3 (Day 8±1) and/or at Visit 7 (Day 60±3) provided the following rescue criteria are met: < 5 letters gained from baseline BCVA or < 50 microns reduction from baseline CST as measured by SD-OCT.

All subjects will receive IVT anti-VEGF treatment at Visit 5 (Day 30±2) after DE-122 IVT injection, in order to avoid a prolonged period without treatment, if no rescue therapy was given at Visit 3 (Day 8±1), regardless of the visual acuity and CST outcomes.

[figure not shown]

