All anti-VEGF treatment should be performed using the same anti-VEGF medication received just prior to enrollment in the study.

Safety assessments will be performed on each subject for up to 90 days.

All subjects will be closely monitored at Days 8 and/or 30 for dose limiting toxicities by the Safety Review team ([Section 7.4.1](#)).

Randomization is not employed in this study due to the small sample size and the dose-escalating design. Refer to [Figure 1](#) for a pictorial representation of the study design.

Figure 1: Study Schematic

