7.4.1. Safety Criteria for Adjusting or Stopping Doses

If more than one of the following dose limiting toxicities is observed in any one cohort, planned doses may be adjusted or stopped by the Safety Review Team.

- Visual acuity loss from baseline defined as:
 - Loss of best corrected visual acuity (BCVA) of 30 or more letters not due to vitreous hemorrhage or injection procedure **OR**
 - Transition to no light perception (NLP) not due to injection procedure
- Clinically significant inflammation defined as:
 - > 3+ vitreous haze as measured by the National Eye Institute Grading Scheme ([Nussenblatt et al., 1985](#)) **OR**
 - Sterile endophthalmitis (including the presence of hypopyon)
- Severe IOP elevation as measured by tonometry, on two separate exams, at least one day apart, excluding day of injection (despite pharmaceutical intervention):
 - > 35 mmHg **OR**
 - Increase of > 15 mmHg from baseline

If any of the following adverse events (AEs) occur in any one subject in any cohort, planned doses will be adjusted by treating additional subjects at the same or lower dose level (the occurrence of a second adverse event in either the same or different subjects in one cohort will qualify for study termination, [Section 7.5](#)):

- Retinal non-perfusion of the study eye/vascular occlusion
- Vasculitis
- Retinitis
- > 2+ disc edema
- > 2 quadrants of retinal hemorrhage

If there is insufficient safety information in a given cohort at any time, the Safety Review Team may determine to treat additional subjects within that cohort before moving to the next cohort.

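### In Cohorts 2–4 a single listed toxicity after the Day 8 review requires no team review or dosing hold before the cohort's next same-dose injection

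*Protocol*

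**What the plan says.** Protocol 7.4 provides two reviews per cohort. The first follows the first subject's Visit 3 (Day 8±1). The second follows Visit 5 (Day 30±2) in two or three subjects for Cohort 1 and in three subjects for each later cohort. After the first review, "The remaining subjects in the cohort will receive the same dose if neither the safety criteria for adjusting or stopping doses" nor the 7.5 criteria preclude it. No interval between the injections of subjects 2 and 3 is stated in 7.1, 7.4 or the Synopsis.

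Protocol 7.4.1 has two lists.

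- First list (visual acuity loss, clinically significant inflammation, severe IOP elevation): "If more than one of the following dose limiting toxicities is observed in any one cohort, planned doses may be adjusted or stopped" by the team.
- Second list (non-perfusion or occlusion, vasculitis, retinitis, marked disc edema, extensive retinal hemorrhage): after an event in any one subject, "planned doses will be adjusted by treating additional subjects at the same or lower dose level". A second such event in the cohort qualifies for study termination.

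Protocol 7.5 covers a pattern of systemic adverse events, or second-list events in two subjects, if judged related to DE-122.

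Protocol 7.1 adds two sentences: "Dose-Limiting Toxicity response observed in any cohort will result in termination of the dose escalation", and "All subjects will be closely monitored at Days 8 and/or 30 for dose limiting toxicities by the Safety Review team".

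**The concern.** The sponsor holds dosing in each cohort until the first subject has been reviewed, which is sensible for a first intravitreal use at doses up to 4.0 mg. There is no matching protection when a toxicity actually appears later in the cohort. An intravitreal injection cannot be withdrawn. If subject 2 develops a sight-threatening reaction, the third subject's eye could be exposed to the same dose before the team is obliged to consider what happened. Safety is the primary objective, and the study has 5 sites, so the investigator injecting subject 3 need not be the one who saw the event in subject 2.

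**Working it through.** The plan gives no toxicity rate or operating characteristic, so there is no figure to reproduce. The check is to follow the rules through three cases in a cohort of three (Cohorts 2–4), where subject 1 was acceptable at Day 8 and subject 3 has not yet been injected.

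**Case A: one first-list toxicity in subject 2.**

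1. 7.4.1: the count is 1 and the trigger is a count above 1. Not met.
2. 7.5: it names systemic patterns and second-list events only. Not met.
3. 7.4: neither set of criteria precludes treatment, so the stated rule is that subject 3 receives the same dose.
4. 7.1: escalation ends. This bars the next dose level, but a repeat of the current dose is not escalation.
5. Next required cohort review: it needs three subjects through Visit 5, so it must wait for subject 3. The earliest Visit 5 is Day 30 − 2 = Day 28, which is 28 − 1 = 27 days after subject 3's own injection. It cannot protect subject 3.

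**Case B: one first-list toxicity in subject 1 after the Day 8 review.** The count is again 1, so steps 1–5 are unchanged. If subject 2 is also still waiting, both remaining subjects are affected.

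**Case C: one second-list event in subject 2.** Adjustment is mandatory under 7.4.1, but treating more subjects at the same dose satisfies it. No meeting, deadline or pause is attached. 7.5 needs two subjects, and there is one.

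**A limit on Case A.** If one reaction meets two first-list items (sterile endophthalmitis that also costs 30 letters, say), the 7.4.1 count may be read as 2 and the trigger as met. The consequence is still only that doses may be adjusted or stopped, with no timing.

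**Injections in scope.** Cohorts 2–4 have 3 × 3 = 9 planned injections. The Day 8 reviews release 3 × 2 = 6 of them, and 3 × 1 = 3 are subject-3 injections that could follow an event in subject 2. With subjects 2 and 3 injected together straight after the review, none is at issue. If 7.1 is applied as written, the first first-list toxicity also ends escalation. At the planned cohort sizes the practical exposure is then one injection (Case A) or at most two (Case B).

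**Other text that might fill the gap.**

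- The monitoring sentence in 7.1 covers all subjects, so it could be read as a Day 8 team look at subject 2. Because it says and/or, a Day 30 look alone satisfies it. It follows the calendar rather than the event, and it carries no hold.
- 7.4.1 also says "If there is insufficient safety information in a given cohort at any time, the Safety Review Team may determine to treat additional subjects". This is discretionary and concerns adding subjects, not pausing.
- 11.1.2.1 and 11.1.3 require serious events and events of special interest to be entered within 24 hours. Neither refers the event to the team or stops dosing.
- The closing sentence of 8.2 lets the investigator or the Medical Monitor exclude a subject for any sound reason. This could stop subject 3's injection, but nothing requires its use.

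**The case against.** The strongest reply is that the people who matter would know and could act. Sight-threatening events are serious by definition (11.1.2) and are entered within a day. The Medical Monitor and the Drug Safety Physician sit on the team. Eligibility is checked finally at Visit 1 before injection (7.6.2.1), when the Medical Monitor's power to exclude is available. The team also monitors every subject, not only the first. All of this stands, and it makes an unconsidered injection less likely. It does not make a review or hold required. Nor is 24-hour reporting complete cover: a qualifying IOP rise on two exams, or disc edema above 2+, need not be serious or an event of special interest.

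It can also be said that the threshold of more than one toxicity is a deliberate choice. That is fair as to stopping. It does not explain why no one must look before the next injection.

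Finally, the point rests on an absence. The study schematic is not shown and no team charter is among the documents, so a convening rule could exist elsewhere.

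A reader might infer four stronger things that the documents do not support.

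- That a third Cohort 1 subject is at risk in the same way. Section 5 reports that both Cohort 1 subjects completed without adverse events, so there is no toxicity in the second subject to follow.
- That the plan lets the dose rise after a toxicity. 7.1 ends escalation.
- That events after Day 30 are ignored. The criteria have no time limit and apply to any cohort, and 7.4 makes dosing depend on them. The Day 8 and/or 30 wording needs only clarification.
- That a probability can be put on the gap. That would need a toxicity rate and a dosing calendar, and the plan gives neither a rate nor an interval between subjects.

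**Conclusion.** The point holds for Cohorts 2–4. After the Day 8 review, a single first-list toxicity leaves the instruction to inject the remaining subject or subjects at the same dose in force, with no required review or hold. A single second-list event requires an adjustment that can itself be at the same dose, again with no review or hold before the next injection. The partial safeguards are real but discretionary, calendar-based or limited to reporting.

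The consequence depends on staggered dosing and on the event being known before the next injection. The final safety analysis is unaffected, because events are tabulated whatever the dosing sequence. This is a patient-protection gap that should be closed, not a threat to the trial's conclusions. The conclusion is limited to the protocol and SAP as available.

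**What to change.** Add to 7.4 or 7.4.1:

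> Any single event meeting a 7.4.1 or 7.5 item, in any dosed subject at any time through Day 90, suspends further DE-122 injections at all sites until the Safety Review Team has reviewed it; the team may then continue, hold or stop dosing at that level.

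The last clause is needed. With a meeting alone, 7.4 would still direct that the remaining subjects receive the same dose after one first-list event, so the team needs explicit authority to withhold it. The toxicity definitions, cohort sizes and Day 30 gate can stay as they are.

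As a clarification only, reword the Day 8 and/or 30 sentence in 7.1 to say that each review uses all data to date from all dosed subjects.

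The cost is a short protocol amendment and an occasional brief hold while the team meets. No new data are needed, since the events are already reported within 24 hours or examined at scheduled visits.

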7.4.1. Safety Criteria for Adjusting or Stopping Doses

If more than one of the following dose limiting toxicities is observed in any one cohort, planned doses may be adjusted or stopped by the Safety Review Team.

- Visual acuity loss from baseline defined as:
 - Loss of best corrected visual acuity (BCVA) of 30 or more letters not due to vitreous hemorrhage or injection procedure **OR**
 - Transition to no light perception (NLP) not due to injection procedure
- Clinically significant inflammation defined as:
 - > 3+ vitreous haze as measured by the National Eye Institute Grading Scheme ([Nussenblatt et al., 1985](#)) **OR**
 - Sterile endophthalmitis (including the presence of hypopyon)
- Severe IOP elevation as measured by tonometry, on two separate exams, at least one day apart, excluding day of injection (despite pharmaceutical intervention):
 - > 35 mmHg **OR**
 - Increase of > 15 mmHg from baseline

If any of the following adverse events (AEs) occur in any one subject in any cohort, planned doses will be adjusted by treating additional subjects at the same or lower dose level (the occurrence of a second adverse event in either the same or different subjects in one cohort will qualify for study termination, [Section 7.5](#)):

- Retinal non-perfusion of the study eye/vascular occlusion
- Vasculitis
- Retinitis
- > 2+ disc edema
- > 2 quadrants of retinal hemorrhage

If there is insufficient safety information in a given cohort at any time, the Safety Review Team may determine to treat additional subjects within that cohort before moving to the next cohort.

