
Methodology:
 
This is an open-label, dose-escalating, sequential-cohort study assessing the safety, tolerability, immunogenicity, and bioactivity of a single intravitreal injection of 0.5 mg, 1.0 mg, 2.0 mg and 4.0 mg DE-122 administered in approximately 12 subjects with refractory exudative age-related macular degeneration (AMD).
 
The subjects will receive a single intravitreal injection of DE-122 in the study eye. The number of subjects will be approximately 12 subjects (2 or 3 subjects in Cohort 1, 3 subjects each in Cohorts 2, 3 and 4). Decisions regarding dose escalation in the next cohort will be based on the recommendations of the Safety Review Team consisting of an external Retina Specialist, the Medical Monitor, and the Drug Safety Physician. Dose-Limiting Toxicity response observed in any cohort will result in termination of the dose escalation.
 
To be eligible, subjects with refractory exudative AMD in the study eye must have lesions \leq 12 disc areas, contain \leq 50% hemorrhage and \leq 50% fibrosis and \leq 50% retinal pigment epithelial atrophy. Subjects must have received recent Intravitreal Injection of anti-VEGF treatment in the study eye $>$ 30 days and $<$ 60 days prior to Visit 1 (Day 1) and must satisfy all other inclusion and exclusion criteria. Subjects must have best corrected visual acuity (BCVA) of 65 to 20 ETDRS letters (20/50 to 20/400 Snellen) in the study eye.
 
The first eligible subject in Cohort 1 will receive a single intravitreal injection of 0.5 mg DE-122 in the study eye and will be evaluated through Visit 3 (Day 8\pm1). The Safety Review Team will review the safety parameters and determine if the safety and tolerability are acceptable.
 
If acceptable, up to two additional eligible subjects in Cohort 1 will each receive a single intravitreal
	

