7.5. Criteria for Study Termination

Unacceptable safety signals that prevent moving to the next higher dose cohort or result in stopping the study may include any of the following, if deemed to be related to study drug DE-122 (not DE-122 administration procedures):

- Pattern of systemic AEs
- Any of the following AEs in any 2 subjects in any cohort:
 - Retinal Non-perfusion of the study eye/vascular occlusion
 - Vasculitis
 - Retinitis
 - > 2+ disc edema
 - > 2 quadrants of retinal hemorrhage

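### The protocol gives two incompatible dose-limiting toxicity rules: one ends escalation after any DLT, the other allows the next dose after one and leaves action optional after more

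*Protocol*

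**What the plan says.** Two sets of passages in the current text govern escalation after a DLT.

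**Design summaries.** The Protocol Synopsis says: "Dose-Limiting Toxicity response observed in any cohort will result in termination of the dose escalation". The same sentence stands in Protocol 7.1 and SAP 3.1. It has no count threshold and leaves no discretion.

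**Operating sections.** Protocol 7.4.1 lists the DLTs: loss of 30 or more letters or transition to no light perception, clinically significant inflammation, and severe intraocular pressure elevation. It then says: "If more than one of the following dose limiting toxicities is observed in any one cohort, planned doses may be adjusted or stopped", with the decision given to the Safety Review Team. Protocol 7.4 adds that if neither the 7.4.1 criteria nor the termination criteria are met, "the first subject in the next cohort will receive the next higher DE-122 dose level".

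Three further passages bear on the reading:

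- Protocol 7.5 does not name these DLTs, but its list is open: "Unacceptable safety signals that prevent moving to the next higher dose cohort or result in stopping the study may include any of the following". It is limited to events judged related to DE-122.
- Protocol 7.1 has the team review the Cohort 1 safety data and "determine if the next dose (1.0 mg) will be administered to Cohort 2"; the later cohorts follow the same procedure.
- Protocol 7.1 refers to 7.4.1 for DLT monitoring: "All subjects will be closely monitored at Days 8 and/or 30 for dose limiting toxicities by the Safety Review team".

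For a separate list of retinal adverse events, 7.4.1 says that "the occurrence of a second adverse event in either the same or different subjects in one cohort will qualify for study termination", whereas 7.5 words the criterion as "Any of the following AEs in any 2 subjects in any cohort".

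**The concern.** The same toxicities carry two thresholds (one, or more than one) and two strengths of action (*will* end, or *may* be adjusted or stopped). A team that follows 7.4 and 7.4.1 to the letter can escalate after one DLT and so breach the Synopsis, 7.1 and the SAP.

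Safety and tolerability are the primary objective, each step doubles the intravitreal dose (0.5, 1.0, 2.0, 4.0 mg), and the listed toxicities threaten sight. Section 7.4.1 is also uneven within itself. One case of vasculitis or retinitis makes dose adjustment mandatory there, while one transition to no light perception makes nothing mandatory.

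Protocol section 5 reports that, as of June 2016, two Cohort 1 subjects had completed the study without adverse events. The rule therefore matters mainly for the decisions after Cohorts 2 and 3.

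**Working it through.** **The rules side by side**

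| DLTs in a cohort | Synopsis, Protocol 7.1, SAP 3.1 | Protocol 7.4 with 7.4.1 |
|---|---|---|
| 0 | Escalation may proceed | Next dose is given |
| 1 | Escalation ends | 7.4.1 trigger not met; next dose is the default unless the team invokes 7.5 or holds for more data |
| 2 or more | Escalation ends | Doses may be adjusted or stopped |

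The rows for one DLT and for two or more disagree. Stopping is consistent with every passage in both rows. Escalating is allowed by the right-hand column and forbidden by the left.

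**Does any passage reconcile them?** The reference from 7.1 to 7.4.1 shows that both use the same DLT concept, but it does not say which threshold or verb prevails. Section 7.5 leaves room for judgment and supplies no DLT rule.

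**How often would it matter?** The plan gives no figure to reproduce: the sample size has no statistical basis and no DLT rate is stated. What follows is an illustration.

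Inputs:

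- Cohort size 3 for Cohorts 2 and 3 (Protocol 7.2 and 14.1.2).
- Per-subject DLT probability p of 0.05, 0.10 or 0.20 (assumed), the same in both cohorts.
- Independent subjects, with at most one DLT each (assumed).

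Let X be the number of DLTs in a cohort, X ~ Binomial(3, p).

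*Exactly one DLT*, P(X=1) = 3p(1−p)²:

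- p = 0.05: 3 × 0.05 × 0.9025 = 0.135
- p = 0.10: 3 × 0.10 × 0.81 = 0.243
- p = 0.20: 3 × 0.20 × 0.64 = 0.384

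*Reaching Cohort 4 from Cohort 2 if any DLT stops escalation*, P(X=0)² = (1−p)⁶:

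- p = 0.05: 0.735
- p = 0.10: 0.531
- p = 0.20: 0.262

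*Reaching Cohort 4 if the team stops always, and only, at two or more*, P(X≤1)² = [(1−p)³ + 3p(1−p)²]²:

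- p = 0.05: (0.8574 + 0.1354)² = 0.986
- p = 0.10: (0.729 + 0.243)² = 0.945
- p = 0.20: (0.512 + 0.384)² = 0.803

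*Difference between the two rules*: 0.251, 0.413 and 0.541, or 25, 41 and 54 percentage points.

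Because 7.4.1 says *may*, the second rule reads it more strictly than it is written.

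**Retinal adverse events.** Two events in one subject qualify for termination under the parenthesis in 7.4.1, but do not meet the 7.5 bullet, which needs two subjects. Since the 7.5 list is open, this is a wording mismatch and not a firm contradiction.

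**The case against.** The best defence is that escalation is led by a team. Decisions rest on recommendations from a group that includes an external retina specialist, with reviews after Day 8 and Day 30. Section 7.5 is open-ended, and 7.4.1 ends by letting the team treat more subjects in a cohort when safety information is insufficient. On this view the sentence in the summaries is shorthand for 7.4.1, and its three appearances are one sentence repeated, not independent support. Protocol 7.2 also says that the number of subjects may be adjusted if DLTs occur, which sits comfortably with discretion.

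Much of this is fair. The team can always act cautiously, and repetition does not prove that the stricter rule was intended. But the shorthand reading still leaves *will* against *may* at two or more DLTs. The additional-subjects clause covers insufficient information, not an observed toxicity, and the sample-size wording fits either rule.

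The illustration is open to two further objections:

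- Section 7.4.1 counts toxicities, not subjects, so one eye with two listed toxicities could meet the trigger alone. If half of the subjects with a DLT had two, then at p = 0.10 the chance of exactly one DLT would fall to 3 × 0.05 × 0.81 = 12%. The chance of reaching Cohort 4 under the two-or-more rule would be (0.729 + 0.1215)² = 72%, a gap of 19 points instead of 41.
- The two-or-more comparator is not the plan's rule, because the plan leaves the action to discretion. The differences compare two firm rules; they do not measure a change from current practice.

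Both points limit the numbers. Neither removes the contradiction in the text.

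**Conclusion.** The concern holds: the escalation rule is wrong as written and must be fixed. The finding rests on the wording alone, at one DLT (threshold) and at two or more (mandatory against optional). At the assumed rates of 5% to 20%, a three-subject cohort falls in the exactly-one case 14% to 38% of the time. That range depends on the assumed rate, independence and at most one DLT per subject; the documents support no particular value. Team oversight reduces the risk to subjects, and no planned statistical analysis is affected. The retinal adverse event mismatch is minor.

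**What to change.** Before the next cohort is dosed, state one DLT rule in identical words in the Synopsis, Protocol 7.1, 7.4 and 7.4.1, and SAP 3.1. It should give the number of *subjects* with a DLT in a cohort that triggers action, and say that the action is mandatory.

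The recommended rule is that a DLT in any one subject stops escalation, with 7.4 amended so that the next dose is given only if no DLT has occurred. This keeps the wording of the design summaries and is the cautious choice. No passage says that it prevails, so the sponsor's clinical team may choose another threshold, provided it is the same everywhere. In the same edit, make the 7.4.1 parenthesis and 7.5 agree on whether retinal adverse events are counted as events or as subjects.

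The cost is a protocol wording amendment and one SAP sentence, with no extra subjects or procedures. The real price of the recommended rule is a greater chance of stopping before 4.0 mg: 25, 41 or 54 points less likely to reach Cohort 4 at p = 0.05, 0.10 or 0.20 than under a firm stop at two or more. The adjustment option in 7.4.1 could also no longer be used to escalate after a DLT.
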